6.2.3.3. Guidelines for the Management of Dry Mouth and Stomatitis

Guidelines for the clinical management of dry mouth (xerostomia) and stomatitis are provided in [Table 9](#) and [Table 10](#), respectively.

Table 9: Guidelines for the Management of Dry Mouth (Xerostomia)

General Prophylaxis		
Grade and Definition	Study Drug Management	Medical Management
Grade 1: symptomatic (eg, dry or thick saliva) without significant dietary alteration; unstimulated saliva flow >0.2 mL/min	Continue study drug at current dose.	Sorbitol lozenges PRN
Grade 2: moderate symptoms; oral intake alterations (eg, copious water, other lubricants, diet limited to purees and/or soft, moist foods); unstimulated saliva 0.1 to 0.2 mL/min	Continue study drug at current dose.	Sorbitol lozenges PRN and Cevimeline 30 mg TID or Pilocarpine 5 mg TID
Grade 3: inability to adequately aliment orally; tube feeding or TPN indicated; unstimulated saliva less than 0.1 ml/min	Hold study drug (for up to 28 days), with weekly reassessments of clinical condition. When resolved to Grade ≤ 1 or baseline, restart at 1 dose level below in consultation with the medical monitor.	Sorbitol lozenges PRN and Cevimeline 30 mg TID or Pilocarpine 5 mg TID, orally
Grade 4: life-threatening consequences, urgent intervention indicated	Discontinue study drug.	Evaluation and therapy as clinically indicated

Abbreviations: PRN = when needed; TID = 3 times a day; TPN = total parenteral nutrition

Table 10: General Prophylaxis and Guidelines for the Management of Oral Mucositis

General Prophylaxis		
Guidelines for the Management of Oral Mucositis		
Grade	Study Drug Management	Symptom Management
Grade 1	Continue study drug at current dose.	
 Continue general prophylaxis recommendations Dexamethasone solution (0.5 mg/5mL solution) swish and spit QID or similar solution that is available in your country and lidocaine 2-5% jelly or solution. Consider clotrimazole/nystatin if subjects are at risk of developing oral candidiasis.
Grade 2	
 Consider holding study drug if the subject has other study drug-related concomitant Grade 2 AEs. Hold study drug if the subject was already on symptom management (dexamethasone solution swish and spit and lidocaine 2-5% jelly or solution) for more than a week. If the study drug is withheld, reassess in 1-2 weeks. If this is the first occurrence of toxicity and resolves to \leq Grade 1 or baseline within 2 weeks, restart at same dose. If recurrent event or takes >2 weeks to resolve to \leq Grade 1 or baseline, then restart at 1 dose level below. 	
 Dexamethasone solution (0.5 mg/5mL solution) swish and spit QID or similar solution that is available in your country and lidocaine 2-5% jelly or solution. Consider concomitant etiologies such as oral candidiasis, oral herpes and recommend appropriate anti-fungal or anti-viral agents.
Grade 3	
 Hold study drug, with reassessments of clinical condition in 1-2 weeks. When resolves to \leq Grade 1 or baseline, restart at 1 dose level below in consultation with the medical monitor. 	
 Dexamethasone solution (0.5 mg/5mL solution) swish and spit QID or similar solution that is available in your country and lidocaine 2-5% jelly or solution. Consider pain management strategies. Consider IV hydration.
Grade 4	Discontinue study drug.	Evaluation and therapy as clinically indicated.

AE=adverse event; QID=four times a day.

6.2.3.4. Guidelines for the Management of Dry Skin and Skin Toxicity

Guidelines for the management of dry skin are provided in [Table 11](#).

- **General prophylaxis:**

- Avoid unnecessary exposure to sunlight and excessive use of soap.
- Avoid bathing in excess; use tepid rather than hot water.
- Use moisturizers regularly; apply thick, alcohol-free and oil-in-water based emollient cream on exposed and dry areas of the body.
- Avoid perfumed products, bubble bath, perfumed soaps, and take breaks from shaving.
- Use broad spectrum sunscreen with a skin protection factor (SPF) ≥ 15 .
- Wear cotton clothes next to skin rather than wool, synthetic fibers, or rough clothing.
- Use occlusive alcohol-free emollient creams (jar or tub) for treatment of mild/moderate xerosis.
- For scaly areas, use exfoliants (ammonium lactate 12% or lactic acid cream 12%).

Table 11: Guidelines for Management of Dry Skin

Grade and Definition	Study Drug Management	Medical Management
Grade 1: Dry skin covering less than 10% body surface area (BSA) and no associated erythema or pruritis.	Continue study drug at current dose.	Use fragrance free moisturizing cream or ointment BID over entire body. Use ammonium lactate 12% cream or salicylic acid 6% cream BID over dry/scaly/hyperkeratotic areas such as palms and soles.
Grade 2: Dry skin covering 10 to 30% BSA and associated with erythema or pruritis with limited instrumental activities of daily living (IADL)	Continue study drug at current dose.	Use fragrance free moisturizing cream or ointment BID over entire body. Use ammonium lactate 12% cream or salicylic acid 6% cream BID over dry/scaly/hyperkeratotic areas such as palms and soles. Use zinc oxide 13-40% at night for areas with fissures.
Grade 3: Dry skin covering >30% BSA and associated with pruritis; limiting self-care activities of daily living (ADL).	Hold study drug (for up to 28 days), with weekly reassessments of clinical condition. When resolves to Grade ≤ 1 or baseline, restart at 1 dose level below in consultation with the medical monitor.	Use topical steroid ointment or cream* BID and zinc oxide 13-40% at night for areas with fissures.
Grade 4: Dry skin with life-threatening consequences, urgent intervention indicated.	Discontinue study drug.	Evaluation and therapy as clinically indicated.

Abbreviation: BID = twice a day

*Topical Steroid Ointments: Clobetasol 0.05%, Betamethasone 0.05%, Fluocinonide 0.05%

6.2.3.5. Guidelines for Management of Nail Toxicity (Onycholysis, Onychodystrophy, and Paronychia)

Guidelines for management of nail discoloration/loss/ridging (onycholysis/onychodystrophy) are provided in [Table 12](#). Guidelines for the management of paronychia are provided in [Table 13](#).

Table 12: General Prophylaxis & Guidelines for Management of Nail Discoloration/Loss/Ridging (Onycholysis/Onychodystrophy)

General Prophylaxis		

 Good hygienic practices, keep fingers and toes clean Keep nails trimmed but avoid aggressive manicuring Use gloves for housecleaning and gardening to minimize damage and prevent infection Nail polish and imitation fingernails should not be worn until the nails have grown out and returned to normal Wearing comfortable shoes (wide sized shoes with room for the toes) 		
Guidelines for Management of Nail Discoloration/Loss/Ridging (Onycholysis/Onychodystrophy)		
Grade	Study Drug Management	Symptom Management
Grade 1	Continue study drug at current dose.	
 Continue general prophylaxis recommendations Over the counter nail strengthener OR poly-urea urethane nail lacquer (Nuvail) OR diethylene glycol monoethylether nail lacquer (Genadur) daily. Use non- alcohol-containing moisturizing creams.
Grade 2	
Consider holding study drug with reassessment in 1-2 weeks.
 
If first occurrence and it resolves to \leqGrade 1 or baseline within 2 weeks, restart at same dose.
 
If recurrent event or takes $>$ 2 weeks to resolve to \leqGrade 1 or baseline, then restart at 1 dose level below in consultation with the medical monitor.
	
 Manage as per Grade 1 For signs of infection (periungual edema/erythema/ tenderness or discharge), obtain bacterial cultures, and then start the following: 
 treatment with oral antibiotic for 2 weeks (cefadroxil 500 mg BID, ciprofloxacin 500 mg BID, or sulfamethoxazole/ trimethoprim BID) topical antifungal lacquer daily for 6+ weeks (ciclopirox olamine 8% OR efinaconazole 10% OR amorolfine 5% weekly OR bifonazole/urea ointment daily) Silver nitrate application weekly AND topical antibiotics AND vinegar soaks^a 
AND

Grade 3	
Hold study drug, with reassessment in 1-2 weeks.
 
When resolves to \leqGrade 1 or baseline, restart at 1 dose level below in consultation with the medical monitor.
	
Silver nitrate application weekly AND topical antibiotics AND vinegar soaks.^a
 
For signs of infection (periungual edema/erythema/ tenderness or discharge), obtain bacterial cultures, and then start the following: treatment with oral antibiotic for 2 weeks (cefadroxil 500 mg BID, ciprofloxacin 500 mg BID, or sulfamethoxazole/ trimethoprim BID).
 
For cases of severe/refractory infection consider intravenous antibiotics.
 
Consider dermatological or surgical evaluation.

Grade 4	Discontinue study drug.	Evaluation and therapy as clinically indicated.

^a Vinegar soaks consist of soaking fingers or toes in a solution of white vinegar in water 1:1 for 15 minutes every day. Examples of topical antibiotic ointments: Mupirocin 2%, gentamycin, bacitracin zinc/polymixin B

Table 13: Guidelines for Management of Paronychia

Grade	Study Drug Management	Symptom Management
Grade 1	Continue study drug at current dose.	Topical antibiotics AND vinegar soaks ^a
Grade 2	Continue study drug at current dose. Consider study drug holding if no improvement in 1 to 2 weeks. When resolves to Grade \leq 1 or baseline, restart at same or 1 dose level below in consultation with the medical monitor	Topical antibiotics AND vinegar soaks ^a AND topical antifungal lacquer daily for 6+ weeks (ciclopirox olamine 8% OR efinaconazole 10% OR amorolfine 5% weekly OR bifonazole/urea ointment daily) For signs of infection (periungual edema/erythema/tenderness and/or discharge), obtain bacterial cultures, and then start the following: treatment with oral antibiotic for 2 weeks (cefadroxil 500 mg BID, ciprofloxacin 500 mg BID, or sulfamethoxazole/trimethoprim (Bactrim) DS BID).
Grade 3	Hold study drug (for up to 28 days), with weekly reassessments of clinical condition. When resolves to Grade \leq 1 or base line, restart at 1 dose level below in consultation with the medical monitor.	Vinegar soaks ^a AND consider nail avulsion For signs of infection (periungual edema/erythema/tenderness and/or discharge), obtain bacterial cultures, and then start the following: treatment with oral antibiotic for 2 weeks (cefadroxil 500 mg BID, ciprofloxacin 500 mg BID, or sulfamethoxazole/trimethoprim (Bactrim) DS BID). For cases of severe/refractory infection consider intravenous antibiotics. Consider dermatological and/or surgical evaluation.

Abbreviations: ADL = activities of daily living; BID = twice daily; DS = double strength

^a Vinegar soaks consist of soaking fingers or toes in a solution of white vinegar in water 1:1 for 15 minutes every day. Examples of topical antibiotic ointments: Mupirocin 2%, gentamycin, bacitracin zinc/polymixin B

6.2.3.6. Guidelines for Eye Toxicity Associated With Vision Changes

Following Amendment 5, after end of study data collection timepoint has been achieved, the eCRF will be closed and only eye events that meet criteria for SAE (eg, hospitalization) will be reported through the company safety repository.

Guidelines for eye toxicity associated with vision changes are provided in [Table 14](#).

Corneal or retinal abnormalities for subjects receiving erdafitinib are considered AEs of special interest. If a subject experiences an event of confirmed new corneal or retinal abnormality while on study drug, these occurrences should be reported as AEs, or as SAEs if the severity is Grade 3 or higher. Any new and clinically significant symptoms, such as, but not limited to, blurred vision, partial or complete loss of vision, double vision, floaters or color spots or halos around light, change in color or night vision, photophobia, ocular pain or stinging sensation, or foreign body sensation should be further evaluated and managed per the guidelines below.

Amsler grid (illustrated in [Attachment 5](#)): For any positive Amsler grid test, the subject should be referred for a full ophthalmologic examination within 7 days. However, if the subject has an abnormal Amsler grid test and otherwise normal ophthalmologic exam at baseline (during Screening), a repeat ophthalmologic examination would be recommended only if, in the opinion of the investigator, there is a likelihood of significant change from the subject's baseline Amsler grid test at Screening, or the subject has developed new clinical symptoms.

Table 14: Guidelines for Management of Eye Toxicity

Grade and Definition	Study Drug Management	Medical Management
Grade 1: Asymptomatic or mild symptoms; clinical or diagnostic observations only or abnormal Amsler grid test	
Refer for an ophthalmologic examination. If an ophthalmologic exam cannot be performed within 7 days, withhold treatment of erdafitinib until an examination can be performed.
 
If there is no evidence of eye toxicity on ophthalmologic examination, continue erdafitinib therapy at the same dose level.
 
If diagnosis from ophthalmologic examination is keratitis or retinal abnormality such as CSR/RPED, withhold erdafitinib until signs and symptoms have resolved.
 
If toxicity is reversible (complete resolution or stabilization and asymptomatic) in 4 weeks according to ophthalmologic examination, resume erdafitinib therapy at the next lower dose level after consultation with the medical monitor.
 
Retinal pigment epithelial detachment, if observed, should be monitored at approximately 2 to 3-week intervals until resolution.
 
Monitor for recurrence every 1 to 2 weeks for a month and as clinically appropriate thereafter. If there is no recurrence then re-escalation can be considered in consultation with the medical monitor.
	
Refer the subject for an ophthalmologic examination.
 
For retinal pathology perform OCT as appropriate and consider referral to a retinal specialist for further evaluation.
 
Follow specific treatment per the ophthalmologist's recommendation.

Grade 2: Moderate; minimal, local or noninvasive intervention indicated; limiting age appropriate instrumental ADL	
Immediately withhold erdafitinib therapy.
 
If there is no evidence of drug-related corneal or retinal pathology on ophthalmologic examination, withhold erdafitinib until signs and symptoms have resolved. Resume erdafitinib therapy at the next lower dose level.
 
If diagnosis from ophthalmologic examination is keratitis or retinal abnormality such as CSR/RPED, withhold erdafitinib until signs and symptoms have resolved, stabilized, or subject is lost to follow-up or withdraws consent (which ever happens first).
 
If toxicity is reversible (complete resolution or stabilization and asymptomatic) within 4 weeks according to ophthalmologic examination, resume erdafitinib therapy at the next lower dose level after consultation with the medical monitor.
 
Retinal pigment epithelial detachment, if observed, should be monitored at approximately 2 to 3-week intervals until resolution.
	
Refer subject to an ophthalmologist for evaluation with an ophthalmologic examination.
 
For retinal pathology, perform OCT as appropriate and consider referral to a retinal specialist for further evaluation.
 
Follow specific treatment per the ophthalmologist's recommendation.

Grade and Definition	Study Drug Management	Medical Management
	Monitor for recurrence every 1 to 2 weeks for a month and as clinically appropriate thereafter. If there is no recurrence, then re-escalation can be considered in consultation with the medical monitor.	
Grade 3: Severe or medically significant but not immediate sight-threatening; hospitalization or prolongation of existing hospitalization indicated; disabling; limiting self-care ADL	
If the toxicity is Grade 3, report as an SAE and withhold erdafitinib. If, however the toxicity is Grade 3 and reversible (complete resolution or stabilization and asymptomatic) within 4 weeks and the subject is having clinical benefit, and the investigator and the sponsor's medical monitor agree that re-starting drug is in the best interest of the subject, then erdafitinib therapy may be resumed at 2 dose levels lower if appropriate.
 
Retinal pigment epithelial detachment, if observed, should be monitored at approximately 2 to 3-week intervals until resolution.
 
Monitor for recurrence using appropriate investigations every 1 to 2 weeks for a month and as clinically appropriate thereafter. For cases of recurrence consider permanent discontinuation.
	
Refer subject to an ophthalmologist for evaluation with an ophthalmologic examination.
 
For retinal pathology, perform OCT as appropriate and consider referral to a retinal specialist for further evaluation.
 
Follow specific treatment per the ophthalmologist's recommendation.

Grade 4: Sight-threatening consequences; urgent intervention indicated; blindness (20/200 or worse) in the affected eye	
Permanently discontinue treatment with erdafitinib.
 
Report as an SAE and monitor resolution of the event until complete resolution, stabilization or the subject is lost to follow-up or withdraws consent (which ever happens first).
	
Promptly refer subject to an ophthalmologist for evaluation with an ophthalmologic examination.
 
Follow specific treatment per the ophthalmologist's recommendation.

Abbreviations: ADL = activities of daily living; CSR = central serous retinopathy; OCT = Optical Coherence Tomography; RPED = retinal pigment epithelial detachments; SAE=serious adverse event

6.2.3.7. Guidelines for the Management of Dry Eye

- **General considerations:** Avoid unnecessary exposure to sunlight, use sunglasses in bright light.
- **Prophylactic management:** Frequent use of artificial tear substitutes and ocular demulcents is strongly recommended.
- **Reactive management:**
 - Withhold erdafitinib for Grade 3 toxicity.
 - Artificial tear substitutes if not started, every 4 to 6 hours.
 - Ocular demulcents.
 - Severe treatment-related dry eye should be evaluated by an ophthalmologist.

6.3. Administration of Cetrelimab

In the Phase 1b erdafitinib + cetrelimab cohort and Arm B of Phase 2 (Cycles 1- 4) of the study, cetrelimab will be administered at 240 mg IV Q2W until 1 or more treatment discontinuation criteria are met. The dose of cetrelimab is increased to 480 mg IV Q4W starting at Cycle 5. In the

Phase 1b erdafitinib + cetrelimab + platinum chemotherapy cohort, cetrelimab will be administered at 360 mg IV Q3W until 1 or more treatment discontinuation criteria are met.

The first infusion should be administered over 60 (± 10) minutes. In the absence of infusion-related reactions, subsequent infusions may be administered intravenously over 30 (-5/+10) minutes. Study drug is to be administered under the supervision of site staff. For the first infusion, vital signs should be monitored before the start of the infusion, every 15 to 20 minutes during the infusion, at the end of infusion (EOI), and 2 hours (± 15 min) after the end of infusion. After the completion of the first infusion, the subject may be discharged if considered clinically stable and all other study procedures have been completed. During subsequent infusions of cetrelimab, vital signs should be monitored pre-dose, once during infusion, and at the end of infusion. On days in which both erdafitinib and cetrelimab will be administered, oral erdafitinib should be given before the start of cetrelimab IV infusion. On days in which erdafitinib + cetrelimab + platinum (cisplatin or carboplatin) chemotherapy will be administered, oral erdafitinib should be given prior to cetrelimab, followed by platinum (cisplatin or carboplatin) chemotherapy IV infusion. Refer to the Investigational Product Preparation Instructions (IPPI)/SIPPM for detailed instructions on drug preparation, storage, and administration.

6.3.1. Retreatment Criteria for Cetrelimab

Before each administration of study drug, the subject will be evaluated for possible toxicities that may have occurred since the previous dose. Chemistry and hematology should be assessed according to the Time and Events Schedule and laboratory results and general physical status must be reviewed prior to administration of cetrelimab. If immune-related toxicity has occurred, the criteria outlined in Section 6.3.4 must be followed for management. Treatment with cetrelimab may continue as long as the criteria for discontinuation of study drug as presented in Section 6.3.3 and Section 10.2 are not met. The criteria for retreatment are outlined Table 15.

Table 15: Retreatment Criteria for Cetrelimab

[figure not shown]
Adverse Event	Requirements before each study agent administration
ANC	$\geq 1.0 \times 10^9/L$ to be stable with or without growth factor support for 5 days
Platelet count	$\geq 50.0 \times 10^9/L$ with or without platelet transfusions, thrombopoietic cytokines, or both
Hemoglobin	$\geq 8.0 \text{ g/dL}$ with or without transfusion, erythropoietin, or both
Fasting glucose, if prompted by HbA1c	$\leq 250 \text{ mg/dL}$ (13.9 mmol/L)
Hyperthyroidism, Hypothyroidism	Grade ≤ 2
AST and ALT	$\leq 3 \times \text{ULN}$ (or $\leq 5 \times \text{ULN}$ for subjects with tumor involvement in the liver)
Total bilirubin	$\leq 1.5 \times \text{ULN}$
Rash	Grade ≤ 2
Other clinically significant toxicity	Recovery to Grade ≤ 1 or baseline

Abbreviations: ALT = alanine aminotransferase; ANC = absolute neutrophil count; AST = aspartate aminotransferase; HbA1c = hemoglobin A1c; ULN = upper limit of normal

If fasting glucose results are available and meet the retreatment criteria, the HbA1c result does not need to be reviewed prior to dosing, but should still be collected.

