6.3.3. Cetrelimab Associated Toxicities Leading to Discontinuation of Study Treatment

A subject must discontinue cetrelimab if:

- The investigator believes that for treatment-emergent toxicity it is in the best interest of the subject to discontinue study treatment
- Grade 4 toxicities except for endocrinopathies that are controlled with replacement hormones
- Grade 2 or 3 immune-related AEs (irAEs) that persist despite treatment modifications or corticosteroid dosing cannot be reduced to ≤ 10 mg prednisone or equivalent per day within 12 weeks

- A treatment-related AE does not resolve to Grade ≤ 1 within 12 weeks of the last dose of study drug unless otherwise agreed to by the sponsor medical monitor and the investigator based on evidence of clinical benefit
- Any non-hematological treatment-related event occurs a second time at Grade ≥ 3 severity
- Grade ≥ 3 (or recurrent Grade 2) pneumonitis
- Grade ≥ 3 nephritis with creatinine ≥ 3 xULN
- Grade ≥ 3 elevation of AST or ALT > 5 xULN or total bilirubin > 3 xULN
- For subjects with baseline Grade 2 elevation of AST or ALT due to liver metastasis, only Grade ≥ 3 elevations that are $\geq 50\%$ of baseline for ≥ 7 days will require discontinuation of study treatment
- Liver metastasis with baseline Grade 2 elevation of AST or ALT, hepatitis with AST or ALT increase $\geq 50\%$ and lasts ≥ 1 week
- Grade ≥ 3 IRRs
- Immune-mediated encephalitis.

If a subject's cetrelimab is discontinued, this will not result in automatic withdrawal of the subject from the study. The subject may continue on the other study treatments(s). Following cetrelimab discontinuation, the subject should complete the End-of-Treatment Visit as described in Time and Events Schedule and Section 9.1.3. Once a subject discontinues treatment, the subject may not be retreated with the study drug.

Following Amendment 5 and after end of study data collection timepoint has been achieved, the eCRF will be closed and only SAEs must be reported through the company safety repository.

6.3.4. Guidelines for Management of Immune-Related Adverse Events and Adverse Events of Clinical Interest

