9.6.2. Clinical Laboratory Tests

Blood samples for serum chemistry and hematology will be collected according to the cohort-specific Time and Events Schedule. More frequent clinical laboratory tests may be performed, as indicated by the overall clinical condition of the subject and for abnormalities that warrant more frequent monitoring.

The investigator must review the laboratory report, document this review, and record any clinically relevant changes occurring during the study in the AE section of the eCRF. Laboratory test results completed on C1D1 should be reviewed prior to dosing and subjects should continue to meet eligibility requirements per the Inclusion/Exclusion criteria.

The following tests will be performed (locally):

Hematology Panel

- hemoglobin
- platelet count
- white blood cell count and ANC only

Serum Chemistry Panel

-albumin	-magnesium
-sodium	-AST, ALT
-calcium	-total bilirubin
-alkaline phosphatase	-lipase
-potassium	-total amylase
-creatinine	-HbA1c ^a
	-glucose ^b

^a If fasting glucose results are available and meet the retreatment criteria, the HbA1c result does not need to be reviewed prior to dosing but should still be collected.

^b fasting glucose at screening and then only as clinically indicated.

Phosphate (PO₄)

Parathyroid hormone (PTH)

Thyroid Panel

-TSH	-T3 (Triiodothyronine)
-FT4 (free thyroxine)	

Serology at Screening Only

- HIV antibody

- Hepatitis B virus surface antigen (HBsAg) and core (HBc) antibody: if positive, further testing of quantitative levels to rule out active infection is required.
- Hepatitis C virus (HCV) antibody: if positive, further testing quantitative levels to rule out active infection is required.

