 - Grade 2 or higher peripheral neuropathy per NCI-CTCAE version 5.0.
 - Grade 2 or higher hearing loss per NCI-CTCAE version 5.0,
- **OR**
 - ECOG PS 2

7. Criterion modified per Amendment 2

7.1 Criterion modified per Amendment 3

7.2 ECOG PS Grade of (see [Attachment 3](#)) as defined below:

Phase 1b erdafitinib + cetrelimab cohort: ECOG 0-2

Phase 1b erdafitinib + cetrelimab + platinum chemotherapy cohort: ECOG 0-1 for cisplatin and ECOG 0-2 for carboplatin.

Phase 2: ECOG 0-2

8. Criterion modified per Amendment 1

8.1 Criterion modified per Amendment 2

8.2 Criterion modified per Amendment 3

8.3 Adequate organ function at Screening defined as follows:

- Phase 1b erdafitinib + cetrelimab cohort and **Phase 2**

Hematology	
Bone marrow function (without the support of cytokines or erythropoiesis-stimulating agent in preceding 2 weeks)	
Hemoglobin	$\geq 8.0 \text{ g/dL} (\geq 5 \text{ mmol/L})$ (without transfusion or demonstrate stability, ie; no significant decline in hemoglobin, for 2 weeks after transfusion)
Platelets	$\geq 75 \times 10^9/\text{L}$
Absolute Neutrophil Count (ANC)	$\geq 1.5 \times 10^9/\text{L}$
Chemistry	
AST and ALT	$\leq 2.5 \times$ upper limit of normal (ULN) or $\leq 5 \times$ ULN for subjects with liver metastases
Creatinine clearance (mL/min)	Calculated using the Cockcroft-Gault formula (Attachment 8) Phase 1b erdafitinib + cetrelimab cohort: $\geq 30 \text{ mL/min}$ Phase 2: $\geq 30 \text{ mL/min}$. If the subject is considered cisplatin-ineligible based on creatinine clearance then CrCl must also be $< 60 \text{ mL/min}$.
Total bilirubin	$\leq 1.5 \times$ ULN or direct bilirubin \leq ULN for subjects with total bilirubin levels $> 1.5 \times$ ULN
Thyroid panel: TSH, T3 or Free T3 (FT3) and Free thyroxine (FT4)	All within normal range. If TSH is not within normal limits, the subject may still be eligible if total T3 or free T3 and free T4 are within normal limits.
Phosphate	Below institutional ULN within 14 days of treatment and prior to C1D1 (medical management allowed)
Cardiovascular	
Left ventricular ejection fraction	Within normal institutional limits

Abbreviations: ALT=alanine aminotransferase; ANC=absolute neutrophil count; AST=aspartate aminotransferase; QTcF=QT corrected interval by the Fridericia's formula; ULN=upper limit of normal

Phase 1b erdafitinib + cetrelimab + platinum (cisplatin or carboplatin) chemotherapy cohort

Hematology	

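### Table 15 bars cetrelimab re-dosing at a total bilirubin that inclusion criterion 8.3 accepts and that reaches no bilirubin stopping rule

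*Protocol*

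**What the plan says.** **Entry.** Inclusion criterion 8.3 (section 4.1 of Appendices 1, 2 and 3) accepts total bilirubin up to 1.5 × ULN. It also accepts direct bilirubin at or below ULN "for subjects with total bilirubin levels" above 1.5 × ULN. Section 9.6.2 says of the Cycle 1 Day 1 laboratory results that "subjects should continue to meet eligibility requirements per the Inclusion/Exclusion criteria".

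**Retreatment.** Table 15 in 6.3.1 gives "Requirements before each study agent administration". The bilirubin row is a single limit of 1.5 × ULN. The AST/ALT row allows 3 × ULN, or 5 × ULN "for subjects with tumor involvement in the liver". Only the row for other clinically significant toxicity lets a subject qualify by returning to baseline.

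**Stopping.** Section 6.3.3 requires cetrelimab to be discontinued for Grade 3 or higher "elevation of AST or ALT > 5 xULN or total bilirubin > 3 xULN". A further bullet begins "For subjects with baseline Grade 2 elevation of AST or ALT due to liver metastasis, only Grade" and restricts stopping to Grade 3 or higher elevations that reach 50% of baseline for at least 7 days. The bullet after it begins "Liver metastasis with baseline Grade 2 elevation of AST or ALT, hepatitis with AST or ALT increase" and sets 50% for at least a week, without naming a grade.

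**The concern.** Three rules cover the same laboratory value, and one does not fit the other two. Entry recognises that a raised total bilirubin with normal direct bilirubin need not bar treatment. The stopping rule leaves room up to 3 × ULN. The retreatment row drops the entry allowance, so a subject can be enrolled, receive a first dose, and then be refused every later dose with no change in liver function.

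What is at stake is exposure to the combination in Arm B and in the Phase 1b cohorts, and consistency between sites. A site that follows Table 15 literally withholds cetrelimab. A site that relies on the sentence in 6.3.1 allowing treatment to go on while no discontinuation criterion is met would continue.

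**Working it through.** The plan gives no figure to reproduce. The check passes bilirubin values through the three rules and counts the doses affected.

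**1. The gap.** Take a subject with direct bilirubin at or below ULN.

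| Total bilirubin (× ULN) | Inclusion 8.3 | Table 15 (at most 1.5) | 6.3.3 stop (above 3) |
|---|---|---|---|
| 1.5 | passes | passes | not met |
| 1.6 | passes | fails | not met |
| 2.0 | passes | fails | not met |
| 3.0 | passes | fails | not met |
| 3.1 | passes | fails | met |

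The gap runs from just above 1.5 to 3.0 × ULN. When direct bilirubin is above ULN, total bilirubin over 1.5 × ULN fails inclusion, so no mismatch arises. The problem is confined to the direct-bilirubin route.

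**2. Doses affected in Arm B.** Appendix 3, section 6.1 gives cetrelimab every 2 weeks in Cycles 1 to 4, with 4-week cycles: 4 × 2 = 8 doses. Eligibility governs Cycle 1 Day 1, so 8 − 1 = 7 later doses fail if bilirubin does not change, and fewer if it falls. The four-weekly doses from Cycle 5 face the same check.

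**3. Is bilirubin the odd row out?** Table 15 against inclusion 8.3:

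| Parameter | Entry | Table 15 |
|---|---|---|
| ANC (× 10⁹/L) | at least 1.5 | at least 1.0 |
| Platelets (× 10⁹/L) | at least 75 (platinum cohort 100) | at least 50 |
| Hemoglobin (g/dL) | at least 8.0 (platinum cohort 9.0) | at least 8.0 |
| AST/ALT (× ULN) | at most 2.5; 5 with liver metastases | at most 3; 5 with liver involvement |
| Total bilirubin (× ULN) | at most 1.5, or direct bilirubin at or below ULN | at most 1.5 |

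Bilirubin is the only one of these rows stricter at retreatment than at entry, and only because the alternative is missing.

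**4. The 50% wording in 6.3.3.** Let b be baseline AST or ALT in × ULN; entry caps b at 5. Read as a value, 50% of baseline is at most 0.5 × 5 = 2.5 × ULN. Every elevation above 5 × ULN exceeds that, so the clause would do nothing. Read as a rise, the threshold is 1.5b, for example 1.5 × 4 = 6.0 and 1.5 × 5 = 7.5 × ULN. Only the rise reading gives the clause work to do.

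**The case against.** **Table 15 concerns adverse events.** Its left-hand column is headed as adverse events, and 6.3.1 opens with toxicity arising since the previous dose. An unchanged entry value is neither new nor worse, so one could say the row does not apply to it. But the row sets an absolute limit before each dose, and relief for a baseline value is written only in the residual row for other toxicity. The header permits a lenient reading without securing it.

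**Section 6.3.2 is redacted.** The Amendment 5 log shows that 6.3.1 to 6.3.3 were revised together for endocrinopathies, so 6.3.2 contains working delay criteria and may contain a bilirubin exception. This stands and lowers confidence.

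**The strictness may be deliberate.** A tighter limit during combination treatment is a possible clinical choice. The protocol gives no sign of one, and the comparable AST/ALT liver allowance is kept.

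**Stronger readings that a reader might infer.** One is that the bilirubin mismatch ends cetrelimab for good, because 6.3.3 forbids retreatment after discontinuation. That rule concerns discontinuation; failing Table 15 withholds a dose. Another is that 6.3.3 gives two competing AST/ALT thresholds through its 50% clause. The value reading makes the clause empty and the next bullet speaks of an increase, so the rise reading is the sensible one. A third is that the two bullets contradict each other. The second is tied to hepatitis and can stand as a separate, diagnosis-based trigger. Any overlap needs 1.5b ≤ 5, that is b ≤ 5 / 1.5 = 3.33 × ULN, and its lower end depends on a Grade 2 boundary that the protocol does not print.

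**Conclusion.** The bilirubin point holds, as a minor one, with moderate confidence. Followed as written, Table 15 withholds cetrelimab from an eligible subject whose bilirubin has not changed and who meets no bilirubin stopping rule. The range is total bilirubin above 1.5 and up to 3 × ULN with direct bilirubin at or below ULN, and up to 7 of the first 8 Arm B doses are affected.

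This assumes that the value stays at baseline, that eligibility governs the first dose, and that the redacted 6.3.2 has no exception. Few subjects are likely to be involved, and other study treatment may continue. Sample size and the planned estimation of response are untouched.

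On AST and ALT the documents support a wording correction and no more.

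**What to change.** Add to the bilirubin row of Table 15: *or direct bilirubin at or below ULN for subjects enrolled with total bilirubin above 1.5 × ULN*. If 6.3.2 already holds an equivalent exception, a cross-reference in Table 15 is enough.

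The cost is one line of text and a direct bilirubin result before dosing in the few subjects enrolled by that route, because the chemistry panel in 9.6.2 lists only "total bilirubin".

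As a separate wording correction, have the 50% clause in the 6.3.3 bullet on baseline Grade 2 AST or ALT read at least 50% above baseline. Leave the two AST/ALT bullets separate and their thresholds unchanged. A merged rule of a 50% rise for 7 days would stop cetrelimab at 1.5 × 3.1 = 4.65 × ULN without hepatitis for a baseline of 3.1, and at 7.5 × ULN for a baseline of 5. Setting those thresholds is a clinical decision, beyond a drafting correction.
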